11.4.2 Analysis of the Key Secondary Endpoints

The key secondary endpoints analysis will follow the testing strategy described in Section 11.2.

Change from baseline in MMDs (Weeks 1-12)

The endpoint will be analysed using the same MMRM model as that described for the primary analysis, except that the test will be based on the estimated mean MMDs, which is averaged over Weeks 1 to 4 (Month 1), Weeks 5 to 8 (Month 2), and Weeks 9 to 12 (Month 3). The estimates will be presented with p-values and 95% CIs.

The change from baseline in MMDs (Weeks 1-12) will be estimated as the average across the 3 4-week intervals, and the treatment effect will be calculated from the least squares estimates from the MMRM model for the month*treatment interaction via a contrast: (1/3, 1/3, 1/3, -1/3, -1/3, -1/3) comparing the effect of EPTI to the effect of PBO across Weeks 1-12.

Change from baseline in MHDs (Weeks 1-4)

Change from baseline in MHDs (Weeks 1-12)

The week 4 endpoint will be analysed using the same methodology as that described for the primary analysis, except that the test be based on the number of MHDs. The baseline MMDs will be replaced with baseline MHDs. The estimates will be presented with p-values and 95% CIs.

For the Weeks 1-4 endpoint, the comparison will be the contrast between EPTI and PBO averaged across Weeks 1-4. For the Weeks 1-12 endpoint, the estimated mean difference in change from baseline in MHDs on EPTI and PBO will be averaged over Weeks 1 to 4 (Month 1), Weeks 5 to 8 (Month 2), and Weeks 9 to 12 (Month 3).

Not fulfilling the ICHD-3 diagnostic criteria for CM nor MOH (Weeks 1-4)

Not fulfilling the ICHD-3 diagnostic criteria for CM nor MOH (Weeks 1-12)

The ICHD-3 diagnostic criteria for CM and/or MOH will be checked at Baseline, Week 4, Week 8, and Week 12 according to the IHS ICHD-3 criteria in the Section 3.9 and the endpoints, including the Weeks 1-12 endpoint, will be derived based on the description in the Section 15.1.6. Missing data after pro-rating will not be used in the analysis. Same manner will be applied to the derivation of Weeks 13-24 endpoint in Open-label Period. The treatment effect of these two endpoints will be analysed using logistic regression with baseline MMDs as a covariate, and treatment group, country and previous treatment failures (≤ 2 , > 2) as categorical variables based on the eDiary data collected over Weeks 1-4 and over Weeks 1-12 separately. The logistic regression model will be fitted using the maximum likelihood (ML) method and the logit link function. The odds ratios for EPTI compared to PBO will be estimated from the model and presented with p-values based on the likelihood ratio test and 95% CIs based on the profile likelihood. In case of convergence, sparsity or separation issues, refer to Section 15.15 for pooling rule.

Change from baseline in average Daily Pain assessment score (Week 1-2)

Daily pain assessment data will be collected in the headache eDiary via the question “*What was the worst pain intensity of this headache today?*”. The pain intensity assessment is collected on a 3-point scale: Mild (score = 1), Moderate (score = 2) and Severe (score = 3).

For each day, the daily pain assessment score will be derived by averaging the worst pain intensity over all headaches of that day. For days on which no headache takes place during the relevant period, the daily pain score will be given as a score of 0. The average daily pain score will be calculated using the daily pain assessments collected during Weeks 1-2. For data

handling details, see Section 15.1.7. Change from baseline in average Daily Pain will be analysed using an ANCOVA with the average Daily Pain at baseline as a covariate and including treatment group, country, and previous treatment failures, as categorical variables. The estimates will be presented with p-values and 95% CIs.

Change from baseline in monthly days with acute migraine medication use (Weeks 1-4)

Change from baseline in monthly days with acute migraine medication use (Weeks 1-12)

The week 4 endpoint will be analysed using the same methodology as that described for the primary analysis, except that the test will be based on monthly days with acute migraine medication use. The baseline MMDs will be replaced with monthly acute migraine medication use at baseline. The estimates will be presented with p-values and 95% CIs. For the week 12 endpoint, the estimated mean difference of monthly days with acute migraine medication uses on eptinezumab and placebo will be averaged over Weeks 1 to 4 (Month 1), Weeks 5 to 8 (Month 2), and Weeks 9 to 12 (Month 3). All medication collected in the eDiary as acute migraine medication regardless of whether they are taken to stop headache/migraine attacks will be accounted for in the analysis.

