3.9.1 Definition of CM based on eDiary data

To evaluate whether a participant fulfils the CM criteria during a specific post-baseline 4-week period, we will use the eDiary data for that month (28-day period) and follow the steps below.

Step 1: Count number of monthly headache days.

If MHD ≥ 15 days in the reported month, then continue to Step 2.

Step 2: Count number of monthly migraine days

At least 8 monthly migraine days using definition of migraine day from [3.6.1](#) are needed for a participant to fulfil the CM criteria.

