11.4.3 Rationale for Selected Analysis Method for the Key Secondary Endpoints

The rationale for the selected analysis method for change from baseline in monthly days with use of acute migraine medication (Weeks 1-4, Weeks 1-12) and change from baseline in MHDs (Weeks 1-4, Weeks 1-12) is covered by Section 11.3.3.

The logistic regression model has been chosen for all the binary key secondary endpoints due to its ability to provide estimates of treatment effects, adjusting for the effects of strata and covariates. Covariates are included in the model based on an approach including key factors representing trial design features/strata (stratum and treatment group), and baseline MMDs to account for its predictive ability for the response.

To compare the equality of two treatment effects in daily pain assessment score for Weeks 1-2, ANCOVA has been chosen to incorporate the covariate information of the analysis for one timepoint comparison.

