11.5 Analysis of Secondary Endpoints

For the Placebo-controlled Period, the secondary endpoints will be summarized by treatment group based on the FAS. For the Open-label Period, the secondary endpoints will be summarized by treatment sequence based on the APTS-OL.

For analyses related to eDiary, estimands follow the same rationale and strategies to address intercurrent events in Section 11.3.1 for continuous endpoints or Section 11.3.1. for binary endpoints in Placebo-controlled Period.

- Migraine on the day after dosing (Day 1) will be derived according to the descriptions in Section 15.1.3 and will be analysed using an extended Cochran-Mantel-Haenszel (CMH) test, adjusting for country and previous treatment failures (≤ 2 , > 2). The estimated proportions for EPTI and PBO will be presented.

The following binary endpoints for the Placebo-controlled Period will be analysed using logistic regression test including country and previous treatment failures as stratification variables (where the stratification variables will indicate the strata used for randomisation), similar to the one used in key secondary analysis in the not fulfilling the ICHD-3 diagnostic criteria for CM nor MOH endpoint.

- Not fulfilling the ICHD-3 diagnostic criteria for CM (Weeks 1-4, Weeks 1-12)
- Not fulfilling the ICHD-3 diagnostic criteria for MOH (Weeks 1-4, Weeks 1-12)
- Not fulfilling the ICHD-3 diagnostic criteria for CM nor MOH (Weeks 13-24) (Only descriptive summaries)

The following continuous endpoints for the Placebo-controlled Period will be analysed using an MMRM model similar to the one used for primary analysis and key secondary analysis, the baseline MMD score will be replaced with the baseline score for the corresponding endpoint in the model.

- Change from baseline in MMDs with use of acute migraine medication (Weeks 1-12)
- Change from baseline in monthly days with triptan or ergotamine medication use (Weeks 1-12)
- Change from baseline in monthly days with individual non-opioid analgesics or NSAID medication use (Weeks 1-12)
- Change from baseline in monthly days with combination non-opioid analgesics medication use (Weeks 1-12)

- Change from baseline in rate of migraines with severe pain intensity (Weeks 1-4, Weeks 1-12)
- Change from baseline in rate of headaches with severe pain intensity (Weeks 1-4, Week 1-12)
- Change from baseline to Weeks 13-24 in MMDs (Only descriptive summaries)

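### The logistic models for CM/MOH status use baseline migraine days as their only baseline diary covariate: a modest, assumption-dependent loss of efficiency

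*SAP*

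**What the plan says.** SAP 11.4.2 states that not fulfilling the criteria for CM nor MOH (Weeks 1-4 and Weeks 1-12) "will be analysed using logistic regression with baseline MMDs as a covariate", with "treatment group, country and previous treatment failures" as categorical terms. SAP 11.4.3 gives the reason for the continuous covariate: "baseline MMDs to account for its predictive ability for the response".

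The outcome is built from diary counts. For CM, SAP 3.9.1 sets two steps: "If MHD ≥ 15 days in the reported month, then continue to Step 2", and then "At least 8 monthly migraine days using definition of migraine day from" SAP 3.6.1. For MOH during the trial, SAP 3.9.2 counts medication days by drug class against 10-day or 15-day thresholds; no migraine-day or headache-day count enters. SAP 15.1.6 scores the composite as a success only if neither condition is met.

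Elsewhere in 11.4.2 the covariate follows the endpoint. For MHDs: "The baseline MMDs will be replaced with baseline MHDs". For acute medication: "The baseline MMDs will be replaced with monthly acute migraine medication use at baseline". SAP 11.5 does the same for the secondary MMRM endpoints, and the binary responder models take baseline MMDs or MHDs. For CM alone and MOH alone, however, 11.5 specifies a model "similar to the one used in key secondary analysis in the not fulfilling the ICHD-3 diagnostic criteria for CM nor MOH endpoint", and 11.6 refers complete withdrawal of acute medication to that same model.

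**The concern.** The SAP justifies its covariate by prediction, but for this family of endpoints it picks only one of the relevant baselines. The mismatch is clearest for MOH alone and complete withdrawal: both are purely medication outcomes, yet by cross-reference both are adjusted for migraine days.

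The composites are Steps 5 and 6 of the fixed sequence in SAP 11.2, so daily pain and the two acute-medication endpoints (Steps 7-9) can be tested only if both succeed. SAP Table 4 lists no sensitivity analysis for the composites, and the sample size section gives no power for them. Any avoidable loss of precision here therefore reduces the chance of reaching Steps 7-9.

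**Working it through.** **1. Outcome components against covariates (SAP 3.9, 11.4.2, 11.5, 11.6, 15.1.6)**

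| Outcome | Diary quantities that decide it | Baseline diary covariate |
|---|---|---|
| Change in MHDs | MHDs | MHDs |
| Change in acute-medication days | acute-medication days | acute-medication days |
| MMD / MHD responders | MMDs / MHDs | MMDs / MHDs |
| CM alone | MHDs, MMDs | MMDs |
| MOH alone | medication days by class | MMDs |
| CM nor MOH | MHDs, MMDs, medication days by class | MMDs |
| Complete withdrawal | any acute medication | MMDs |

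The last four rows are the exception. Migraine on Day 1 is not listed because it is tested by CMH without a baseline covariate.

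**2. The plan's own figure (protocol 16.12, SAP 14)**

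Inputs: difference 1.5, SD 6.2, two-sided 5%, 80% power, 5% not contributing data.

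- n per arm = 2 × (1.960 + 0.842)² × 6.2² / 1.5² = 2 × 7.849 × 38.44 / 2.25 = 268.2, so 269 (stated 270).
- Power at 270 per arm is 80.3%.
- 270 / 0.95 = 284.2, so 285 per arm.

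The figure reproduces, but it concerns the primary endpoint only. No response rate, correlation or power is given for the CM/MOH endpoints, so what follows rests on assumed inputs.

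**3. Simulation of the Weeks 1-4 composite**

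Assumptions, not from the documents except where marked:

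- 270 per arm (documents); 1500 trials per scenario.
- Baseline MHDs, MMDs and medication days normal with means 20.5, 17, 17 and SDs 4, 5, 5, cross-correlation 0.3 or 0.6. They are then truncated to MHDs 15-26 and MMDs ≥ 8 (eligibility, protocol 5.3) and to medication days ≥ 10.
- Follow-up for each measure = m + s + ρ(6.2/SD_B)(B − mean B) + √(1 − ρ²) × 6.2 × e − d × T. Here m is the mean before truncation, s = −4 or −6, d = 1.5 or 2.0 days, and e has cross-measure correlation 0.7. The pairs (d, s) used were (1.5, −6), (1.5, −4) and (2.0, −4).
- Success = not (MHD ≥ 15 and MMD ≥ 8), and medication days < 10 (a single threshold on total days).
- Likelihood-ratio test for treatment at 5%. Country and treatment-failure strata not simulated.

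The resulting success rates were about 23-37% on placebo and 32-47% on eptinezumab. Ranges over six scenarios per correlation ρ:

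| ρ | Power, MMDs only | + MHDs | + MHDs and medication days | Total gain, points |
|---|---|---|---|---|
| 0.2 | 63.3-86.2% | 64.0-86.3% | 64.2-86.1% | −0.2 to +0.9 |
| 0.4 | 61.4-87.5% | 62.0-88.0% | 63.7-89.1% | +1.7 to +3.3 |
| 0.6 | 63.8-89.7% | 65.1-90.6% | 69.7-93.1% | +3.4 to +6.4 |

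The gain is computed within scenario. Monte Carlo error is about √(0.7 × 0.3 / 1500) = 1.2 points per power figure; the paired differences are more precise.

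Example (cross-correlation 0.3, ρ = 0.6, d = 1.5, s = −4): 63.8% with MMDs, 65.1% adding MHDs (+1.3), 69.7% adding medication days (a further +4.6). Across all scenarios MHDs alone add at most 1.8 points (70.7% to 72.5%).

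**4. A separate, smaller simulation**

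This used 600 trials per scenario, 270 per arm and ρ = 0.3, 0.5, 0.6.

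- Composite: 84.5, 83.2, 87.0% became 85.5, 85.2, 89.0%, gains of 1.0, 2.0 and 2.0 points.
- MOH alone: 61.5, 63.0, 62.3% became 65.3, 68.0, 69.7%, gains of 3.8, 5.0 and 7.4 points.

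Monte Carlo error is up to √(0.63 × 0.37 / 600) = 2.0 points per figure, so these are rough.

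**The case against.** The best defence is that this is a prespecified and explained covariate choice. The protocol synopsis already names baseline MMDs for the binary key secondary endpoints, SAP 11.4.3 gives the reason, and SAP 18.5.2 and 18.5.4 declare the added country factor and the move to logistic regression throughout. Each continuous endpoint has one natural baseline to swap in; the composite has none. Total acute-medication days is also an imperfect stand-in. MOH uses class-specific thresholds for medication taken to treat a headache, whereas the acute-medication endpoint counts all acute medication, whether or not taken to stop an attack. Finally, entry criteria confine baseline MHDs to 15-26 and require overuse during screening, which limits what these baselines can predict.

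Most of this stands as a limit on size. Range restriction makes low correlations more plausible; the correlation in the simulation is defined within the eligible population, so this bears on which row of the table applies. The lack of a single natural baseline explains the choice for the composite. It does not explain MOH alone or complete withdrawal, where the criterion contains no migraine days.

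Two stronger readings are tempting and should be resisted. A reader might infer that the model adjusts for migraine days and nothing else, or that it ignores what defines the outcome. In fact country and previous treatment failures are included, and MMDs are the second CM step. A reader might also infer that the strongest predictors have been dropped. The documents contain no covariate-outcome associations from which to rank them.

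**Conclusion.** The point holds as one of efficiency. Baseline MMDs are the only baseline diary covariate in the CM/MOH logistic models, they bear on only the CM component, and the SAP's own practice for its other modelled diary endpoints would bring in the rest.

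For the Weeks 1-4 composite the loss is about 0 points of power at a baseline-to-follow-up correlation near 0.2 and up to about 6 points at 0.6, mostly from acute-medication days. Every input behind that range other than the sample size, the SD of 6.2 borrowed from the primary endpoint, the 1.5-day effect and the eligibility limits is assumed. The Weeks 1-12 composite (Step 6) was not simulated in the main check, so no figure is offered for it.

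The larger gain for MOH alone, 4-7 points in one simulation, should not be read as a threat to the hierarchy: that endpoint is outside the nine steps. Nor do the documents support reading the omission as bias or as a threat to type I error. Treatment is randomised, and leaving out a prognostic baseline does neither.

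**What to change.** Prespecify before unblinding:

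- **CM nor MOH (11.4.2):** keep baseline MMDs, country and previous treatment failures; add baseline MHDs and baseline monthly acute-medication days.
- **MOH alone (11.5) and complete withdrawal of acute medication (11.6):** use baseline acute-medication days as the diary covariate.
- **CM alone (11.5):** use baseline MHDs and MMDs.

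State the covariates explicitly in 11.5 and 11.6 so they are not inherited by cross-reference, and record the change in section 18.

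The cost is a few sentences. SAP 3.1, 7.3 and 15.1 already provide all three baselines. The odds ratio becomes conditional on one or two more covariates. It is already conditional on MMDs, country and previous failures, so Estimands 2a and 2b in Table 3 need only a clause naming the conditioning set. Total medication days remains a proxy for the class-specific counts, and the SAP should say so. If the data have already been unblinded, the revised model can be reported only as a labelled supplementary analysis.

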11.4.3 Rationale for Selected Analysis Method for the Key Secondary Endpoints

The rationale for the selected analysis method for change from baseline in monthly days with use of acute migraine medication (Weeks 1-4, Weeks 1-12) and change from baseline in MHDs (Weeks 1-4, Weeks 1-12) is covered by Section 11.3.3.

The logistic regression model has been chosen for all the binary key secondary endpoints due to its ability to provide estimates of treatment effects, adjusting for the effects of strata and covariates. Covariates are included in the model based on an approach including key factors representing trial design features/strata (stratum and treatment group), and baseline MMDs to account for its predictive ability for the response.

To compare the equality of two treatment effects in daily pain assessment score for Weeks 1-2, ANCOVA has been chosen to incorporate the covariate information of the analysis for one timepoint comparison.

11.4.4 Sensitivity Analysis of the Key Secondary Endpoints

For the key secondary endpoints change from Baseline in MMDs (Weeks 1-12), change from baseline in MHDs (Weeks 1-4, Weeks 1-12), and change from baseline in monthly days with use of acute migraine medication (Weeks 1-12), pMI will be conducted similarly to the first sensitivity analysis described for the primary endpoint, see Section 11.3.4.

For the change from baseline in average Daily Pain Assessment (Weeks 1-2), the sensitivity analysis will be conducted using the same ANCOVA model in Section 11.4.2 but we will derive the average daily pain assessment score on the days without taking any acute migraine medications. For data handling details, see Section 15.1.7.

11.4.5 Exploratory Analysis of the Key Secondary Endpoints

- Change from baseline in the number of MMDs using the alternative definitions of migraine day (Weeks 1-12)

- Change from baseline in the number of MHDs using the alternative definitions of migraine day (Weeks 1-4, Weeks 1-12)
- Not fulfilling the ICHD-3 diagnostic criteria for CM nor MOH (Weeks 1-4, Weeks 1-12)

Two additional exploratory analyses using the alternative definitions of migraine day (1) based on daily symptoms and duration of the headache and (2) considering a mixture of headache day and migraine day in Section 3.6.1 to count and derive the MMDs/MHDs will be conducted to evaluate the relevance of the different derivation strategies. The same models will be applied as those used for the primary definition of a migraine/headache day.

11.5 Analysis of Secondary Endpoints

For the Placebo-controlled Period, the secondary endpoints will be summarized by treatment group based on the FAS. For the Open-label Period, the secondary endpoints will be summarized by treatment sequence based on the APTS-OL.

For analyses related to eDiary, estimands follow the same rationale and strategies to address intercurrent events in Section 11.3.1 for continuous endpoints or Section 11.3.1. for binary endpoints in Placebo-controlled Period.

- Migraine on the day after dosing (Day 1) will be derived according to the descriptions in Section 15.1.3 and will be analysed using an extended Cochran-Mantel-Haenszel (CMH) test, adjusting for country and previous treatment failures (≤ 2 , > 2). The estimated proportions for EPTI and PBO will be presented.

The following binary endpoints for the Placebo-controlled Period will be analysed using logistic regression test including country and previous treatment failures as stratification variables (where the stratification variables will indicate the strata used for randomisation), similar to the one used in key secondary analysis in the not fulfilling the ICHD-3 diagnostic criteria for CM nor MOH endpoint.

- Not fulfilling the ICHD-3 diagnostic criteria for CM (Weeks 1-4, Weeks 1-12)
- Not fulfilling the ICHD-3 diagnostic criteria for MOH (Weeks 1-4, Weeks 1-12)
- Not fulfilling the ICHD-3 diagnostic criteria for CM nor MOH (Weeks 13-24) (Only descriptive summaries)

The following continuous endpoints for the Placebo-controlled Period will be analysed using an MMRM model similar to the one used for primary analysis and key secondary analysis, the baseline MMD score will be replaced with the baseline score for the corresponding endpoint in the model.

- Change from baseline in MMDs with use of acute migraine medication (Weeks 1-12)
- Change from baseline in monthly days with triptan or ergotamine medication use (Weeks 1-12)
- Change from baseline in monthly days with individual non-opioid analgesics or NSAID medication use (Weeks 1-12)
- Change from baseline in monthly days with combination non-opioid analgesics medication use (Weeks 1-12)

- Change from baseline in rate of migraines with severe pain intensity (Weeks 1-4, Weeks 1-12)
- Change from baseline in rate of headaches with severe pain intensity (Weeks 1-4, Week 1-12)
- Change from baseline to Weeks 13-24 in MMDs (Only descriptive summaries)
- Change from baseline to Weeks 13-24 in MHDs (Only descriptive summaries)
- Change from baseline to Weeks 13-24 in monthly days with acute migraine medication use (Only descriptive summaries)
- Change from baseline to Weeks 13-24 in monthly days with triptan or ergotamine medication use (Only descriptive summaries)
- Change from baseline to Weeks 13-24 in monthly days with individual non-opioid analgesics or NSAID medication use (Only descriptive summaries)

For the following endpoints based on response rates, treatment effects of EPTI compared to PBO will be analysed using logistic regression. The model will include baseline MMDs or MHDs as a continuous covariate, and treatment, country and previous treatment failures as factors. The logistic regression model will be fitted using the maximum likelihood (ML) method and the logit link function. For handling of missing MMD and MHD values, see Section 15.1.2. The odds ratios for EPTI compared to PBO will be estimated from the model and presented with p-values based on the likelihood ratio test and 95% CIs based on the profile likelihood. In case of convergence, sparsity or separation issues, refer to Section 15.15 for the pooling rule.

- Response: $\geq 50\%$ reduction from baseline in MMDs (Weeks 1-4, Weeks 1-12)
- Response: $\geq 75\%$ reduction from baseline in MMDs (Weeks 1-4, Weeks 1-12)
- Response: $\geq 50\%$ reduction from baseline in MHDs (Weeks 1-4, Weeks 1-12)
- Response: $\geq 75\%$ reduction from baseline in MHDs (Weeks 1-4, Weeks 1-12)

The following endpoints based on health-related quality of life scores test between EPTI and PBO at Week 4, Week 12 will use the similar MMRM model defined in the primary analysis. The baseline MMD score will be replaced with the baseline score for the corresponding endpoint in the model:

- Change from baseline to Week 4 and Week 12 in the HIT-6 total score
- Change from baseline to Week 4 and Week 12 in the mMIDAS total score
- Change from baseline to Week 4 and Week 12 in the MSQ v2.1 sub-scores (Role Function-Restrictive, Role Function-Preventive, Emotional Function)
- Change from baseline to Week 4 and Week 12 in the EQ-5D-5L VAS score
- Change from baseline to Week 12 in the WPAI:M sub-scores (Absenteeism, Presenteeism, Work productivity loss, Activity impairment)
- Change from baseline to Week 4 and Week 12 in HADS – depression, and anxiety subscale scores

- TSQM-9 score at Week 4 and Week 12 (Effectiveness, Convenience, Overall Satisfaction) (exclude baseline covariate in the model)
- PGIC score at Week 4 and Week 12 (exclude baseline covariate in the model)

The endpoint based on MBS scores test between EPTI and PBO at Week12 will use similar ANCOVA model defined in the analysis of key secondary endpoint: change from baseline in average Daily Pain assessment score.

- MBS score at Week 12 (exclude baseline covariate in the model)

The following endpoints based on diary data and health-related quality of life scores between EPTI-EPTI and PBO-EPTI will be summarized by descriptive tables.

- Change from baseline to Week 24 in average Daily Pain assessment score
- Change from baseline to Week 24 in the HIT-6 total score
- Change from baseline to Week 24 in the mMIDAS total score
- Change from baseline to Week 24 in the MSQ v2.1 sub-scores
- Change from baseline to Week 24 in the EQ-5D-5L VAS score
- Change from baseline to Week 24 in the WPAI:M sub-scores
- Change from baseline to Week 24 in HADS sub-scores
- TSQM-9 sub-scores at Week 24
- PGIC score at Week 24
- MBS score at Week 24

Descriptive tables displaying the distribution of answers to the items in HCRU at each visit will be provided by treatment group.

